10.8.1 Adverse Event Reporting

All adverse events will be recorded from the time the consent form is signed through 30 days following completion of pembrolizumab treatment. SABR related adverse events will be followed at each follow-up visit until 2 years after completion of SABR.

All adverse events, which occur whilst the participant is enrolled on the trial (including the follow-up phase), must be reported in the patients' medical records and recorded on the Adverse Events CRF. The Common Terminology Criteria for Adverse Events (CTCAE version 4.03 – see appendices) or other more specific AE tools must be used to grade the severity of an event. Laboratory values need reporting as AEs only if abnormal and deemed clinically significant by the investigator

All adverse events must be recorded on the Adverse Events CRF with the following information:

- The severity grade using CTCAE version 4.03
- Its relationship to the study drug(s)
- Treatment changes
- Whether it constitutes a serious adverse event (SAE)

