9.1.18.2 Dose Modification

Adverse events (both non-serious and serious) associated with pembrolizumab exposure may represent an immunologic etiology. These adverse events may occur shortly after the first dose or several months after the last dose of treatment. Pembrolizumab must be withheld for drug-related toxicities and severe or life-threatening AEs as per Table 6 below.

See Section 9.3.1 for supportive care guidelines, including use of corticosteroids.

Table 6: Dose Modification Guidelines for Drug-Related Adverse Events

Toxicity	Hold Treatment For Grade	Timing for Restarting Treatment	Treatment Discontinuation
Diarrhea / Colitis	2-3	Toxicity resolves to Grade 0-1	Toxicity does not resolve within 12 weeks of last dose or inability to reduce corticosteroid to 10 mg or less of prednisone or equivalent per day within 12 weeks
	4	Permanently discontinue	Permanently discontinue
AST, ALT, or Increased Bilirubin	2	Toxicity resolves to Grade 0-1	Toxicity does not resolve within 12 weeks of last dose
	3-4	Permanently discontinue (see exception below) ^a	Permanently discontinue
Type 1 diabetes mellitus (if new onset) or Hyperglycemia	T1DM or 3-4	Hold pembrolizumab for new onset Type 1 diabetes mellitus or Grade 3-4 hyperglycemia associated with evidence of beta cell failure	Resume pembrolizumab when patients are clinically and metabolically stable
Hypophysitis	2-4	Toxicity resolves to Grade 0-1. Therapy with pembrolizumab can be continued while endocrine replacement therapy is instituted	Toxicity does not resolve within 12 weeks of last dose or inability to reduce corticosteroid to 10 mg or less of prednisone or equivalent per day within 12 weeks
Hyperthyroidism	3	Toxicity resolves to Grade 0-1	Toxicity does not resolve within 12 weeks of last dose or inability to reduce corticosteroid to 10 mg or less of prednisone or equivalent per day within 12 weeks
	4	Permanently discontinue	Permanently discontinue
Hypothyroidism		Therapy with pembrolizumab can be continued while thyroid replacement therapy is instituted	Therapy with pembrolizumab can be continued while thyroid replacement therapy is instituted
Infusion Reaction	2 ^b	Toxicity resolves to Grade 0-1	Permanently discontinue if toxicity develops despite adequate premedication
	3-4	Permanently discontinue	Permanently discontinue

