9.1.20 Trial Blinding/Masking

This is an open-label trial; therefore, the Sponsor, investigator and participant will know the treatment administered.

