10.7 Assessing and Recording Adverse Events

An adverse event is defined as any untoward medical occurrence in a patient or clinical investigation participant administered a pharmaceutical product (or any other protocol specified intervention including radiation therapy, surgery or use of a device) and which does not necessarily have to have a causal relationship with this treatment. An adverse event can therefore be any unfavourable and unintended sign (including an abnormal laboratory finding, for example), symptom, or disease temporally associated with the use of a medicinal product or protocol-specified procedure (including radiation therapy, surgery or use of a device), whether or not considered related to the medicinal product or protocol-specified procedure.

Any worsening (i.e., any clinically significant adverse change in frequency and/or intensity) of a pre-existing condition that is temporally associated with the use of the medicinal product, (or associated with the use of any other protocol specified intervention including radiation therapy, surgery or use of a device), is also an adverse event.

Adverse events may occur during the course of the use of protocol treatment in clinical trials or within the follow-up period specified by the protocol, or prescribed in clinical practice, from overdose (whether accidental or intentional), from abuse and from withdrawal.

Adverse events may also occur in screened participants during any pre-allocation baseline period as a result of a protocol-specified intervention, including washout or discontinuation of usual therapy, diet, placebo treatment or a procedure.

Progression of the cancer under study is not considered an adverse event unless it is considered to be drug related by the investigator.

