11.2.3 Safety analysis

Safety will be assessed using CTCAE v4.03 and the maximum toxicity grade of each adverse event will be derived and presented in table format. The proportion of patients who suffer from grade 3 or higher toxicities (each toxicity and overall) will be provided along with its exact 95% CI for all patients who have received at least one dose of pembrolizumab and completed at least one SABR treatment. Events of clinical interest will be also tabulated (see Section 10.8.5.3 Events of Clinical Interest).

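### An isolated grade 3+ laboratory value that the investigator judges not clinically significant drops out of the primary safety rate, and no planned laboratory table would recover it

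*Combined protocol and SAP*

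**What the plan says.** Four provisions decide whether a laboratory abnormality reaches the primary result.

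- **Definition (10.7).** An adverse event can be any unfavourable sign, "including an abnormal laboratory finding, for example". No test of significance is attached.
- **Recording (10.8.1).** "Laboratory values need reporting as AEs only if abnormal and deemed clinically significant by the investigator". The protocol does not define the term and sets no grade above which a value must be recorded.
- **Analysis (11.2.3).** "the maximum toxicity grade of each adverse event will be derived and presented in table format", and "The proportion of patients who suffer from grade 3 or higher toxicities (each toxicity and overall) will be provided" with an exact 95% confidence interval. Events of clinical interest are tabulated as well. No analysis of the laboratory values themselves is planned.
- **Blinding (9.1.20).** "This is an open-label trial; therefore, the Sponsor, investigator and participant will know the treatment administered".

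The notes to the Schedule of Events call for laboratory tests before every pembrolizumab cycle, covering haematology, chemistry, liver, renal and thyroid function. Gradable values will therefore exist for the whole treatment period.

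**The concern.** The primary objective is to describe the safety profile, and its headline statistic is the share of patients with grade 3 or higher toxicity. For laboratory toxicity, entry to that statistic depends on a judgement by an investigator who knows the treatment, and that judgement can remove events but never add them. Two investigators could see the same grade 3 value, one following 10.7 and the other 10.8.1, record it differently, and both believe they had complied.

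With a single arm, no comparator is filtered in the same way, so the level of the estimate is the result. The serious adverse event route does not clearly close the gap, because the definition in 10.8.5 starts from something already classed as an adverse event or adverse drug reaction. At stake is the completeness of the safety description on which a larger randomized study would be based.

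**Working it through.** **Step 1: trace a value through the text.** Take a grade 3 laboratory value that is isolated, is judged not clinically significant and leads to no change in treatment.

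| Provision | Is the value captured? |
|---|---|
| 10.7, definition | Yes: it may be an adverse event |
| 10.8.1, recording | No: it need not be reported |
| 10.8.5.3, event of clinical interest | Only if AST or ALT is at least 3 times the upper limit of normal, with bilirubin at least 2 times and alkaline phosphatase below 2 times at the same time |
| 9.1.18.2, Table 6 | Not engaged, because nothing was held or stopped |
| 11.2.3, primary proportion | No: built from recorded adverse events |
| 11.2.3, laboratory table | None planned |

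A transaminase rise without the bilirubin component, a creatinine rise or a cytopenia can therefore be absent from every planned safety output.

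**Step 2: reproduce the plan's own figures.** For x of n = 30 patients, the exact (Clopper-Pearson) limits are

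- lower = Beta quantile (0.025; x, n − x + 1)
- upper = Beta quantile (0.975; x + 1, n − x)

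For x = 6 this gives 7.7% to 38.6%, and Table 8 prints 8% to 39%. All 12 rows of Table 8 agree after rounding.

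The stopping probability in 11.2.10 also reproduces. With 12 patients and a true rate of 5%, P(2 or more) = 0.1184 for each toxicity, and 1 − (1 − 0.1184)² = 0.223, against the stated 22%. Its triggers are pneumonitis and bowel toxicity, neither of which is defined by a laboratory value.

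**Step 3: size of an omission.** One patient is 1/30 = 3.3 points of the overall rate, provided that patient has no other recorded grade 3+ event. The documents give no count of such patients, so both the reported count and the omitted count below are assumptions.

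| Reported | Rate (exact 95% CI) | 1 omitted | 2 omitted | 3 omitted | 4 omitted |
|---|---|---|---|---|---|
| 3/30 | 10.0% (2.1–26.5) | 13.3% (3.8–30.7) | 16.7% (5.6–34.7) | 20.0% (7.7–38.6) | 23.3% (9.9–42.3) |
| 6/30 | 20.0% (7.7–38.6) | 23.3% (9.9–42.3) | 26.7% (12.3–45.9) | 30.0% (14.7–49.4) | 33.3% (17.3–52.8) |
| 9/30 | 30.0% (14.7–49.4) | 33.3% (17.3–52.8) | 36.7% (19.9–56.1) | 40.0% (22.7–59.4) | 43.3% (25.5–62.6) |

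For a single laboratory toxicity, the condition of no other grade 3+ event falls away. Reporting 0/30 (upper limit 11.6%) when two patients had it would hide a rate of 6.7% (0.8% to 22.1%).

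**The case against.** The strongest reply is that the values most exposed to the filter matter least: isolated abnormalities that nobody treated or acted on. Several provisions support this. Section 10.1.15 has the investigator review laboratory results before each dose. Section 10.1.7 applies the same significance test to physical findings, so this is a consistent recording convention. The combined hepatic pattern must go on the adverse event form whatever the investigator thinks of it. The study is descriptive, with no success threshold on the grade 3+ rate.

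Much of this stands, and it rules out three stronger readings that a reader might infer.

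- **That a value can hold or end pembrolizumab and still not be an adverse event.** The documents do not support this. Table 6 is titled "Dose Modification Guidelines for Drug-Related Adverse Events", so an event acted on under it has already been classed as one, and the adverse event form records treatment changes. Nor does Table 6 act broadly on bare laboratory grades. The row "AST, ALT, or Increased Bilirubin" is worded as laboratory results, but the glucose row requires new-onset type 1 diabetes or evidence of beta cell failure, and the renal row is a diagnosis. What remains is that no sentence says explicitly that a value leading to a hold or discontinuation must be recorded.
- **That the loss falls mainly on immune toxicity.** Section 9.3.1 calls for corticosteroids for hepatic and renal events from grade 2 when they are attributed to pembrolizumab. An event treated in that way has been judged significant.
- **That open-label judgement biases a comparison.** There is only one arm, so the issue is the level of the estimate.

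The reply does not remove the remaining gap. A CTCAE grade 3+ proportion that leaves out some CTCAE grade 3+ findings, on an undefined criterion, is not what a reader of the result would assume.

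**Conclusion.** The point holds in a limited form. Sections 10.7 and 10.8.1 disagree on when a laboratory abnormality is an adverse event. Because 11.2.3 relies on recorded events alone, an isolated grade 3+ value judged not significant is lost from the primary rate. The direction is certain, since the filter can only lower the rate. The size is unknown: it is 3.3 points for each patient with no other grade 3+ event, or 3.3 to 13.3 points for one to four such patients, and those counts are assumed. Nothing in the documents shows that any patient will be omitted, so none of these figures is a corrected rate. The sample size, Table 8 and the stopping rule need no change. The amendment is worth making because it concerns the completeness of the primary endpoint and the remedy is small.

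**What to change.** 1. **Reconcile 10.7 and 10.8.1.** State that any CTCAE v4.03 grade 3+ laboratory value, and any laboratory value that leads to a hold or discontinuation of pembrolizumab, is recorded as an adverse event. The significance judgement can stay for lower grades. This is a recording rule only and alters no dose rule.
2. **Add laboratory tables to 11.2.3.** Derive the CTCAE v4.03 grade by program from the per-cycle tests. Tabulate the worst post-baseline grade and the shift from baseline. The shift is needed because the eligibility limits in Table 3 admit some patients with values already outside normal.
3. **Show the overall grade 3+ proportion twice, each with its exact 95% CI:** as reported by investigators, and with derived grade 3+ laboratory values that are worse than baseline added. The second sits beside the first and does not replace it.

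**Cost.** Some programming is needed. The tests are run by local laboratories, and the documents do not say that numeric results and reference ranges are entered in the EDC. If they are not, data entry is an added burden. The second rate will be equal or less favourable and may count transient values. After treatment, haematology is scheduled only as clinically indicated, so the derived tables will mainly describe the treatment period and should say so.

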10.8.2 Late Toxicities

Late toxicities (AEs) which are deemed by the investigator to be attributed to protocol specified SABR treatment are to be reported on the AE CRF. Late Toxicities are defined as AEs directly attributed by the Investigator to SABR treatment on this study, recorded from 30 days post last MK-3475 treatment until 24 months following the last SABR treatment.

10.8.3 Definition of an Overdose for This Protocol and Reporting of Overdose to the Sponsor and to Merck

For purposes of this trial, an overdose of pembrolizumab will be defined as any dose of 1,000 mg or greater (≥ 5 times the indicated dose). No specific information is available on the treatment of overdose of pembrolizumab. Appropriate supportive treatment should be provided if clinically indicated. In the event of overdose, the participant should be observed closely for signs of toxicity. Appropriate supportive treatment should be provided if clinically indicated.

If an adverse event(s) is associated with ("results from") the overdose of pembrolizumab, the adverse event(s) is reported as a serious adverse event, even if no other seriousness criteria are met.

If a dose of pembrolizumab meeting the protocol definition of overdose is taken without any associated clinical symptoms or abnormal laboratory results, the overdose is reported as a non-serious Event of Clinical Interest (ECI), using the terminology "accidental or intentional overdose without adverse effect" on the Adverse Event CRF page.

All reports of overdose with and without an adverse event must be reported within 24 hours to the Sponsor and within 2 working days hours to Merck Global Safety. (Attn: Worldwide Product Safety; [contact]).

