Whole Blood Sample ^{15,16}		X	X	X		X (9, 12 and 24 months)	X

Clinical/Administrative Assessments

- Vital signs include blood pressure, heart rate, respiratory rate and temperature. Height will be measured at screening only.
- Baseline abnormalities (using CTCAE v4.03) must be recorded from signature of informed consent to prior to start of treatment. Adverse events (using CTCAE v4.03) are then required to be assessed on day 1 of every pembrolizumab cycle and at 30 days following last pembrolizumab treatment. SABR related adverse events will be collected at every subsequent follow-up visit until 2 years after completion of SABR.

3. Conventional hypofractionated radiotherapy of **30-36Gy** may be delivered to individual lesion(s) if SABR is determined to be not technically or safely possible to deliver. If CRT is required it must be completed prior to SABR administration. **At least one lesion must receive SABR.**

4. Pembrolizumab should be administered at 5 days (+/- 3 days) of the last SABR treatment for a total of 8 cycles.

Laboratory Procedures/Assessments – All diagnostic laboratory tests should be performed within 10 days of study registration (to determine eligibility), and also within 3 days prior to every cycle of pembrolizumab (unless indicated otherwise below)

5. Urine or serum pregnancy test for patient of childbearing potential should be performed within 7 days of study registration and also 72 hours within first dose of pembrolizumab. If the urine test is positive or cannot be confirmed as negative, a serum pregnancy test will be required.

6. Haematology: Haematocrit, haemoglobin, platelet count, white blood cell count (total and differential), red blood cell count, absolute neutrophil count and absolute lymphocyte count.

7. Chemistry: Carbon dioxide (if considered standard of care only), uric acid, calcium chloride, glucose, phosphorus, potassium, sodium, magnesium, total protein.

8. Liver Function Tests: Albumin, Alkaline Phosphatase (ALP), Alanine Aminotransferase (ALT), Aspartate Aminotransferase (AST), Lactate Dehydrogenase (LDH), Gamma-Glutamyl Transferase (GGT, total bilirubin and direct bilirubin if total bilirubin is elevated above the ULN), Kidney Function Tests: Urea, creatinine.

9. Thyroid Function: T3, T4 and TSH.

10. Coagulation Profile: PT (INR), aPTT. These need only be done if there is clinical concern regarding patient anticoagulation.

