7.14 Rationale of Endpoints Definition

Primary Endpoint:

Safety (acute and long term) will be evaluated using CTCAE version 4.03 in all patients who have received at least one SABR treatment and one dose of pembrolizumab. Acute adverse events (AE) are defined as AEs occurring from the time of first SABR treatment to 30 days post

end of pembrolizumab treatment and long term AE are defined as AEs occurring after 30 days post end of pembrolizumab treatment.

Secondary Endpoints:

To evaluate effectiveness of the treatment combination, using the following measures:

- a) Overall survival (OS), time to local progression (TTLP), distant progression free survival (DPFS) and overall response rates
 - i. OS will be measured from the date of commencement of SABR treatment to the date of death from any cause.
 - ii. TTLP will be measured from date of commencement of SABR treatment to the date of first local progression. Death and commencement of a further course of systemic therapy will be considered as censoring events.
 - iii. DPFS will be measured from the date of commencement of SABR treatment to the date of first distant progression at site not documented at registration, or date of death from any cause for patients without distant progression. Commencement of second course of a further course of systemic therapy will be considered as censoring event.
- b) Overall response is defined as complete response or partial response, measured using RECIST 1.1 criteria. The RECIST definition of complete response has been modified to include disappearance of the target tumor radiographically or complete metabolic response. The primary is excluded from the evaluation of the overall response.
- c) Disease control is defined as complete response or partial response at any time after treatment commencement or stable disease for at least 6 months, measured using RECIST 1.1 criteria. The RECIST definition of complete response has been modified to include disappearance of the target tumor radiographically or complete metabolic response. The primary is excluded from the evaluation of the disease control.
- d) Pain will be evaluated using the Numerical Pain Rating Scale at the following time points: pre-conventional radiotherapy treatment (if CRT performed), pre-SABR treatment, prior to each cycle of pembrolizumab, then 3 monthly until 24 months after the end of SABR treatment.

Exploratory Endpoints

A number of translational endpoints will be evaluated including:

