9.5 Participant Withdrawal/Discontinuation Criteria

9.5.1 Protocol Treatment Discontinuation

A participant must be discontinued from the trial treatment for any of the following reasons:

- The participant or legal representative (such as a parent or legal guardian) withdraws consent.
- Unacceptable adverse experiences as described in Section 9.1.18: Dose Modifications
- Intercurrent illness that prevents further administration of treatment
- Investigator's decision to withdraw the participant
- The participant has a confirmed positive serum pregnancy test
- Noncompliance with trial treatment or procedure requirements

When a participant discontinues/withdraws treatment prior to trial completion, all applicable activities scheduled for the End of Treatment visit should be performed at the time of discontinuation. Any AEs which are present at the time of discontinuation/withdrawal should be followed in accordance with the safety requirements. After discontinuing treatment (for any reason), participants should attend the site for a 30 day (post end of trial treatment) safety follow-up visit (see Section 10.3) for assessment of AEs and Efficacy.

The End of Treatment and Follow-up visit procedures are listed in The Schedule of Events (Section 2) and Section 10.2: Visit Requirements. After the end of treatment, each participant will be followed for 30 days for adverse event monitoring (serious adverse events will be collected for 90 days after the end of treatment as described in Section 10.8.5 Serious Adverse

Events. Participants who discontinue treatment will have post-treatment follow-up for disease status until initiating a non-study systemic cancer treatment, withdrawing consent or becoming lost to follow-up.

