10.1.10 Adverse Event (AE) Monitoring

The investigator or qualified designee will assess each participant to evaluate for potential new or worsening AEs as specified in the Schedule of Events and more frequently if clinically indicated. Adverse experiences will be graded and recorded throughout the study and during the follow-up period according to NCI CTCAE Version 4.03. AEs will be characterized in terms regarding seriousness, causality, toxicity grading, and action taken with regard to trial treatment.

Please refer to Section 10.7 for detailed information regarding the assessment and recording of AEs.

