10.8.5 Serious Adverse Events

Adverse events and adverse drug reactions are considered 'serious' if they threaten life or function.

SAEs include 'Serious Adverse Drug Reactions'. During clinical investigations, adverse events may occur, which if suspected to be medicinal product related ('adverse drug reactions') might be significant enough to lead to important changes in the way the medicinal product is developed (e.g. change in dose, population, monitoring, consent). This is particularly true for reactions, which in their most severe form threaten life or function.

Due to the significant information they provide, Serious Adverse Events (including Serious Adverse Drug Reactions) require expedited reporting. SAEs are defined as any adverse event or adverse drug reaction which:

- Results in death (i.e. fatal/grade 5 CTC AE)
- Is life-threatening (i.e. grade 4 CTC AE)
- Requires inpatient hospitalisation or prolongation of existing hospitalisation*
- Results in persistent or significant disability/incapacity; or
- Is a congenital anomaly/birth defect
- Is a new cancer (that is not a condition of the study)
- Is associated with an overdose
- Other significant medical event

Note: The term 'life-threatening' in the definition of 'serious' refers to an event in which the participant was immediately at risk of death at the time of event; it does not refer to an event, which hypothetically might have caused death if it were more severe.

*An event that results in hospitalisation or prolongs an existing hospitalisation will not be considered a serious adverse event if the only reason for the hospitalisation or prolongation was:

- Administration of chemotherapy
- Administration of trial procedures
- Placement of a permanent intravenous catheter
- Hospice placement for terminal care
- Pre-trial scheduled elective surgery
- Outpatient hospitalisation for procedures such as:
 - Elective day surgery
 - Convenience purposes (e.g. transportation difficulties)

- Planned admission as part of supportive care for insertion of PEG tube or nasogastric tube for commencement of enteral feeding (i.e. did not occur following urgent admission as a result of weight loss or other patient medical events)

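### The primary endpoint counts every adverse event later than 30 days after pembrolizumab, but the collection rules contradict each other on which are recorded, and Section 11.2.3 does not report the two periods separately

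*Combined protocol and SAP*

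**What the plan says.** **Endpoint.** Section 7.14 makes acute and long-term safety the primary endpoint. Acute AEs run from first SABR to 30 days after pembrolizumab ends; "long term AE are defined as AEs occurring after 30 days post end of pembrolizumab treatment". There is no attribution limit and no end date.

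**Narrow collection sentences.**
- Section 10.8.1, first paragraph: "All adverse events will be recorded from the time the consent form is signed through 30 days following completion of pembrolizumab treatment". After that it follows SABR-related AEs to 2 years.
- Schedule of Events, note 2: "SABR related adverse events will be collected at every subsequent follow-up visit until 2 years after completion of SABR".
- Section 9.5.1: after treatment ends, "each participant will be followed for 30 days for adverse event monitoring", with serious AEs to 90 days.
- Section 10.8.2: "Late Toxicities are defined as AEs directly attributed by the Investigator to SABR treatment on this study", to 24 months after the last SABR.

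**Broad collection sentences.**
- Section 10.1.10: "Adverse experiences will be graded and recorded throughout the study and during the follow-up period".
- Section 10.8.1, second paragraph, requires recording of "All adverse events, which occur whilst the participant is enrolled on the trial (including the follow-up phase".

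**Exit from follow-up.** Schedule note 18 and Section 10.4 restrict follow-up to survival after distant progression, new systemic therapy or pembrolizumab retreatment. Section 10.6 does the same for the last two. Table 1 nevertheless marks AE review in both the Follow-up and the Progression columns.

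**Analysis.** Section 11.2.3 tabulates the maximum grade of each AE and gives grade 3+ proportions, for each toxicity and overall, with exact 95% confidence intervals. It names no period.

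**The concern.** Adjacent paragraphs of Section 10.8.1 give sites different instructions on the primary endpoint. A site that follows the first paragraph, note 2 and Section 9.5.1 in good faith would leave out events that Section 7.14 counts. Section 9.1.18.2 itself expects that pembrolizumab AEs, serious or not, can appear several months after the last dose.

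Attribution is difficult in this combination. Section 7.10 lists radiation pneumonitis as a SABR risk, and Section 11.2.9 lists pneumonitis as an expected pembrolizumab event. Section 10.8 has five causality codes, and Section 10.8.2 does not say which of them amount to direct attribution. Under a SABR-only rule, whether a late pneumonitis is recorded could depend on a judgement between two plausible causes, although the objective is the safety of the combination.

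Under the narrow sentences, the reported proportion would mix all-cause AEs before day 30 with mainly SABR-attributed AEs after it, over unequal follow-up. The expected direction is understatement of long-term toxicity. Late events that sites did not record may not be recoverable at analysis.

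**Working it through.** **1. The plan's own figures.** The Clopper-Pearson interval for 8/30 is 12.28% to 45.89%, against 12%–46% in Table 8; all 12 rows reproduce. For the stopping rule, P(≥2 of 12 at 5%) = 1 − 0.95^12 − 12 × 0.05 × 0.95^11 = 0.118, and 1 − (1 − 0.118)² = 0.223, against the stated 22%. Neither figure is in question.

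**2. Timeline on schedule.** The first dose is 5 days after SABR, with 8 cycles 21 days apart (Section 9.1.18).
- Last dose: 5 + 7 × 21 = day 152.
- Long-term period starts: 152 + 30 = day 182, about month 6.
- 90-day serious AE window, counted from the last dose as in Section 10.8.5, ends: 152 + 90 = day 242, about month 8.
- SABR AE review ends: month 24.

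**3. Routes for a new event after day 182, if a site follows the narrow sentences.**

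| Event | Routine AE record | Other route |
|---|---|---|
| SABR-attributed | Yes, to month 24 | – |
| Serious, any cause, to day 242 | Only if SABR-related | Serious AE report (10.8.5), ending earlier if new anti-cancer therapy starts |
| Serious, treatment-related, after day 242 | Only if SABR-related | Reportable at any time if brought to the investigator's attention (10.8.5) |
| Serious, unrelated, after day 242 | No | None assured |
| Non-serious grade 3, not attributed to SABR | No | None assured, unless it is an event of clinical interest within the window in 10.8.5.3 |

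The serious criteria in Section 10.8.5 are wide: death, grade 4, hospitalisation, disability and other significant medical events. Section 10.3 also follows AEs above grade 1 until they settle or new therapy starts, but it concerns AEs arising before the safety visit. The last two rows are the residual gap. The documents give no rate for these events, so its size cannot be computed.

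**4. Unequal follow-up alone.** Recruitment lasts 24 months, and the final analysis is 12 months after the last SABR (Section 11.2.9). With even accrual (assumed), potential follow-up is uniform from 12 to 36 months. Half the patients, 15 of 30, can reach month 24. Mean observable time in the month 6–24 window is ½ × 12 + ½ × 18 = 15 of 18 months, or 83%.

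Assume a constant hazard h giving risk p over those 18 months, with no exits and no deaths, so h = −ln(1 − p)/18. The expected observed risk is ½p + ½[1 − (e^(−6h) − e^(−18h))/(12h)].
- p = 10% (assumed): 8.4%.
- p = 4% (top of the grade 3–4 range in Section 7.7.3, which is SABR alone and not late-only): 3.3%.

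For the overall proportion, assume an independent acute risk a and use 1 − (1 − a)(1 − late). With a = 20%:
- p = 10%: 26.7% seen against 28.0% true, a shortfall of 0.39 of 30 patients.
- p = 4%: 22.7% against 23.2%, a shortfall of 0.16 of 30.

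With a from 10% to 30%, the shortfall runs from 0.44 to 0.34 patients (p = 10%) and from 0.18 to 0.14 (p = 4%).

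**5. If AE review also stops at exit.** With a constant exit rate (assumed), a 10% late risk would show as 6.5% if 80% remain under review at 12 months, and as 4.6% if 58% remain. The 58% is borrowed from the surveillance cohort in Section 7.9 and is not an estimate for this trial.

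**The case against.** The best defence is that the broad sentences already satisfy Section 7.14. On that view Section 10.8.2 only defines a SABR-attributed subset under its own name. It does not redefine long-term AEs or say that other AEs go unrecorded. That is right about Section 10.8.2 by itself. It does not remove the conflict, because note 2, Section 9.5.1 and the first paragraph of 10.8.1 narrow collection and nothing says which sentence governs.

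A second defence is that the serious AE rules, the events of clinical interest and Section 10.3 catch what matters. They catch much of it, and a reader who infers that late pembrolizumab toxicity goes uncollected would be going too far.

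A third defence is that crude proportions with exact intervals suit a pragmatic study of 30 patients with descriptive aims (Section 11.1). That stands. Section 11.2.3 gives proportions by toxicity as well as overall, so it would be wrong to say that the plan offers a single number, and the absence of a competing-risk analysis is not an error. What remains is that Section 7.14 defines two periods and the analysis section reports neither separately.

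A reader might also infer that the plan is silent on AE review after exit. It is not: survival-only follow-up, read literally, ends that review, while the 24-month SABR review has no exception. This is a contradiction.

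**Conclusion.** The contradiction on AE collection after day 30 is real and touches the primary endpoint. The survival-only rule is a second, separate contradiction. The missing split by period is a drafting gap in Section 11.2.3.

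Severity is minor to moderate. The finding affects how the long-term safety result can be read when the larger study is planned. It does not affect a decision in this trial: the stopping rule uses early events, and Table 8 and the 22% are correct.

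The documents do not support a claim that the safety result will be materially biased. The only part that can be sized, unequal follow-up without exits, is at most about 0.4 of 30 patients under the assumed risks, small beside the 12%–46% interval for 8/30. That figure does not measure the collection gap. Loss through exits could be larger, but depends on a rate the documents do not give.

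**What to change.** 1. **Collection.** Align Schedule note 2, Section 9.5.1, the first paragraph of 10.8.1 and Section 10.8.2 with Sections 7.14, 10.1.10 and the second paragraph of 10.8.1. AEs after day 30 are then recorded regardless of cause, with attribution noted. Give the long-term period in 7.14 an end date; the 24-month limit now appears only in the SABR text. If narrower collection is intended, amend 7.14 to match.
2. **Exit.** Reconcile Schedule note 18 and Sections 10.4 and 10.6 with note 2 and Sections 10.8.1 and 10.8.2 by stating whether AE review continues after distant progression, new therapy or retreatment. If it does, flag those events and report them separately. If not, say that the long-term result covers only the time before exit and that censoring there may be informative.
3. **Analysis.** In Section 11.2.3 report acute and long-term grade 3+ proportions separately, each with an exact interval. As an optional addition, give cumulative incidence at 12 and 24 months after SABR, with 95% confidence intervals, death as a competing event and numbers at risk. Section 11.2.4 already reports at 1 and 2 years.

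The cost is wording changes, a few extra AE entries at existing visits and a small amount of analysis. If AE review continues in survival follow-up, a contact schedule is also needed, because Section 10.5 sets none.
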